10.2 Sample size calculation

10.2.1 Number of subjects calculated

n= 141 evaluable subjects (OU).

47 subjects per group.

10.2.2 Justification of the sample size calculation

The sample size calculation was made based on the study by Pinto-Fraga et al. (2017), where they evaluated the safety and efficacy of an artificial tear of 0.2% hyaluronic acid (HA) versus SS (saline, 0.9% NaCl) in patients with mild dry eye (OSD) after one month of treatment. Subjects treated with HA had a decrease of -19.66% with respect to their initial mean value, while in subjects treated with SS there was a significant increase in the final OSDI score of 12.47%, $p < 0.05$ compared to the initial [61].

For the calculation, a decrease in the OSDI score of 20% was considered for the formulation proposed in this protocol (Multi-dose Lagricel® Ofteno) with respect to its initial mean value in subjects with mild to moderate DED.

The sample size was calculated using the equation for two proportions [62], considering a power of 80% (β), a significance level of 0.05 (α) and a non-inferiority margin (δ) of 10%, based on the following working hypotheses:

$$H_0: P_A - P_B \leq \delta$$

$$H_1: P_A - P_B > \delta$$

Where, δ is the margin of non-inferiority and the ratio between the sample size of the two groups is:

$$k = \frac{n_A}{n_B}$$

The calculation to estimate the sample size and power was done using an online tool and following the equations [63]:

$$n_A = kn_B, n_B = \left(\frac{P_A(1 - P_A)}{k} + P_B(1 - P_B) \right) \left(\frac{z_{1-\alpha} + z_{B-\beta}}{P_A - P_B - \delta} \right)^2$$
$$1 - \beta = \Phi(z - z_{1-\alpha}) + \phi(-z - z_{1-\alpha}), z = \frac{P_A - P_B - \delta}{\sqrt{\frac{P_A(1 - P_A)}{n_A} + \frac{P_B(1 - P_B)}{n_B}}}$$

Where:

- $(k = \frac{n_A}{n_B})$ is the allocation ratio,
- (Φ) is the standard normal distribution function,
- (α) is the Type I error,
- (β) is the Type II error, meaning that $(1 - \beta)$ is the power, and
- (δ) is the test margin.

According to the previous calculation, the result is 39 subjects, this calculation was increased by 20% considering possible losses (8 subjects). The total suggested sample size is 141 subjects (47 subjects per treatment dosage), who will contribute OU to the study.

11. Ethical considerations

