Safety primary outcome variable:

- Incidence of AEs (ET: days 15 and 31).

[figure not shown]
Safety Secondary Outcome Variable:

- Changes in the BCVA (ET: day 15 and 31).
- Changes in intraocular pressure (IOP) (ET: day 15 and 31).

Statistical methodology

The Kolmogorov-Smirnov and Shapiro Wilk tests will be performed, as appropriate, to know if the distribution presents normality in the results obtained in each study group. The data will be expressed with measures of central tendency: mean and standard deviation for the quantitative variables. Qualitative variables will be presented in frequencies and percentages. The statistical analysis will be performed by means of the Analysis of Variance Test (ANOVA) for the quantitative variables for the difference between the groups. The difference between the qualitative variables will be analyzed by means of X² (Chi-square) or Fisher's exact. A 95% CI will be considered for the non-inferiority criteria based on the objectives of the study, an alpha (α) will be considered significant ≤ 0.05

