3.4 Hypotheses

H₀: Multi-dose Lagricel® Ofteno decreases the OSDI test score by 20% or more at the end of the study in at least 1 of the proposed dosages.

H₁: Multi-dose Lagricel® Ofteno does not decrease the OSDI test score by 20% at the end of the study in at least 1 of the proposed dosages.

4. Study design

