7.4 Outcome variables

7.4.1 Primary outcome of efficacy

- OSDI test score (ET: day 31).

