10.1.2 Data interpretation

The Kolmogorov-Smirnov and Shapiro Wilk tests will be performed, as appropriate, to determine if the distribution is normal in the results obtained in each study group [59].

The results of the continuous quantitative variables will be presented in measures of central tendency: mean, standard deviation and/or range.

- Intragroup analysis: Differences within groups will be analyzed using the one-way ANOVA or the Student's t-test when applicable.
- Inter-group analysis: For equal variances, Tukey's post-hoc test will be used, otherwise Dunnett's statistic will be used. Student's t-test will be used when applicable.

The level of difference to consider significance will be an alpha (α) of 0.05 or less. A 95% confidence interval (95% CI) will be considered for non-inferiority criteria [60].

The result of the nominal and ordinal qualitative variables will be presented in frequencies, proportions and percentages.

The statistical analysis to identify significant differences in the qualitative variables will be carried out by creating 2x2 contingency tables and will be carried out as follows:

- Intra-group difference: McNemar test. This is applied to 2x2 contingency tables with a dichotomous feature, with pairs of paired subjects, to determine if the marginal frequencies of row and column are equal (marginal homogeneity).
- Difference between groups: Pearson's Chi-square test (X^2) or Fisher's exact test at expected values less than 5.

The level of difference to consider significance will be an alpha (α) of 0.05 or less.

For the reporting of AEs, all eyes of those participants who were randomly assigned to an intervention group after the baseline visit will be considered. The results will be expressed in number of subjects.

The final report of the results will be shown in tables or graphs, as appropriate.

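### The stated 80% power comes from a two-proportion non-inferiority formula with no stated proportions, so it does not apply to the planned OSDI analysis; separately, 47 per arm is loss-inflated in one place and evaluable in others

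*Combined protocol and SAP*

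**What the plan says.** **Sample size (10.2.2).** The effect assumption is that "a decrease in the OSDI score of 20% was considered for the formulation proposed in this protocol", measured "with respect to its initial mean value in subjects with mild to moderate DED". It is supported by a cited study of 0.2% hyaluronic acid, in which mean OSDI changed by -19.66% on treatment and +12.47% on saline. The method is then "The sample size was calculated using the equation for two proportions", with power 80%, alpha 0.05 and margin 10%. The printed equation uses z at 1 - alpha, so it is one-sided. P_A, P_B and the allocation ratio have no values.

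**Primary outcome and analysis.** Section 7.4.1 makes the OSDI score at day 31 the primary efficacy outcome. Table 3 (7.4.5) classes it as quantitative and assigns ANOVA and Student's t. The Synopsis plans "Analysis of Variance Test (ANOVA) for the quantitative variables for the difference between the groups", and 10.1.2 adds "For equal variances, Tukey's post-hoc test will be used", with Dunnett's statistic otherwise. The Synopsis and 10.1.2 also mention a 95% CI for non-inferiority criteria. The efficacy statement in 3.4 is that the product "decreases the OSDI test score by 20% or more at the end of the study in at least 1 of the proposed dosages".

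**What 47 means.** Section 10.2.2 says "the result is 39 subjects, this calculation was increased by 20% considering possible losses (8 subjects"), giving 47 per dosage and 141 in total. Section 4.3 plans recruitment on 141. The Synopsis, 10.1.4 and 10.2.1 describe the same 141 as evaluable, and 10.1.4 says that number is required.

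**The concern.** A percentage fall in a mean score is not a proportion of subjects, and the documents define no OSDI responder. The sizing formula compares two proportions. The hypothesis in 3.4 concerns the fall within a dosage. The listed ANOVA compares mean scores between three dosages. The 80% belongs to the first of these, while the trial will report the other two. A reader therefore cannot tell what OSDI change, or what difference between dosages, the trial can detect, although 2.5.1 gives its purpose as documenting efficacy and determining the ideal dosage.

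The second defect affects conduct. If 47 per arm already includes losses, recruitment stops at 141. If 47 must be evaluable, recruitment has to go further.

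**Working it through.** **1. The plan's own figure.** With k = 1, the equation in 10.2.2 is

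n = [P_A(1 - P_A) + P_B(1 - P_B)] × [(z(0.95) + z(0.80)) / (P_A - P_B - δ)]², with z(0.95) + z(0.80) = 1.645 + 0.842.

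P_A and P_B are not given, so 39 can only be searched for (one-sided 0.05, 10-point margin):

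| P_A, P_B, δ | n per group |
|---|---|
| 0.20, 0.20, ±0.10 | 198 |
| 0.20, 0.1966, -0.10 / +0.10 | 184 / 211 |
| 0.20, 0.10, +0.10 | undefined (zero denominator) |
| 0.20, 0.10, -0.10 | 0.25 × (2.487/0.20)² = 38.64, so 39 |
| 0.20, 0.35, +0.10 | 38.33, also 39 |

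The 0.20/0.10 pair returns 39 only when the 10-point difference adds to the margin. The proportion 0.10 is stated nowhere, and other pairs also return 39. At one-sided 0.025, which matches a two-sided 95% CI, the same pair needs 50 per group and has 70.5% power at 39.

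**2. The steps after 39.** 39 × 1.2 = 46.8, so 47; 47 × 3 = 141. These reproduce.

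**3. What 39 (47) analysed per arm can detect on a continuous score.** No SD is given, so the results are in SD units, at 80% power and two-sided 5%:

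- Within-arm change against zero, paired t: 0.46 (0.42) SD of change.
- One pair of arms, unadjusted, normal approximation: (1.960 + 0.842) × √(2/n) = 0.63 (0.58) SD.
- Three-arm ANOVA, noncentral F: Cohen's f = 0.291 (0.264). With the middle arm halfway, f = 0.408d, so the extreme arms differ by d = 0.71 (0.65) SD. With one arm different and two equal, f = 0.471d, so d = 0.62 (0.56) SD.

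The halfway pattern is the least favourable for a given range of means. Section 6.1.2.1 expects the middle frequency to be optimal, so neither pattern should be taken as the protocol's own.

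**4. Randomised or evaluable.**

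- 47 randomised, 39 to remain: tolerable attrition is 8/47 = 17.0%. A full 20% loss leaves 47 × 0.8 = 37.6.
- 47 evaluable with 20% loss, by the plan's own rule: 47 × 1.2 = 56.4, so 57 per arm; 171 in total; 171 - 141 = 30 more.
- 47 evaluable with 20% loss, by division: 47/0.8 = 58.75, so 59 per arm; 177 in total; 177 - 141 = 36 more.

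**The case against.** **Non-inferiority is not absent from the analysis.** The Synopsis and 10.1.2 both announce a 95% CI for it, so it would be too strong to say that no such analysis is planned. That stands. However, neither place names a comparator dosage, an OSDI contrast or a margin in OSDI points, so the announcement does not connect the formula to the primary outcome.

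**39 may be correct arithmetic.** It may well come from 0.20 and 0.10. The documents do not show a calculation error, only missing inputs. Even if that pair was used, a percentage change would still have been entered as a proportion.

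**The number is partly reconciled.** Section 10.1.4 refers to a contemplated 20% loss, which points back to 10.2.2, and 5.2.2 and 10.1.4 allow replacement. But replacement is at the sponsor's discretion and covers withdrawal of consent and loss to follow-up. It does not cover subjects removed from the efficacy analysis for adherence below 70% (6.4, 10.1.5).

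**A tempting stronger reading** is that the trial is underpowered. That would need an SD, which is not given, and a between-dosage difference, which the documents never posit: the 20% is a fall from an arm's own baseline. A sound calculation could still support about 47 per arm.

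**Conclusion.** The point holds on both parts and should be fixed. The 80% power and 10% margin do not describe the planned OSDI analysis, and the inputs behind 39 are not stated. The power of the primary analysis is unknown rather than shown to be low. The detectable effects above are scale-free; they assume roughly normal scores, a common SD for the between-arm figures, and 39 or 47 subjects analysed per arm.

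The status of 47 per arm is contradictory. A reader might infer that 30 to 36 subjects are missing from the plan. That follows only if 47 evaluable per arm is really meant. The derivation in 10.2.2 and the recruitment plan in 4.3 point the other way, and the documents do not settle it.

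**What to change.** 1. In 10.2.2, delete the 80% power and 10% margin statement, or restate it for one named primary OSDI contrast: the within-dosage fall of 3.4, or a difference between named dosages. Give a sourced SD, a difference or margin in OSDI points, the sidedness and the matching CI level.
2. If no SD can be sourced, state the detectable effect for 39 (47) analysed per arm at 80% power, two-sided 5%: 0.46 (0.42) SD of within-arm change; 0.63 (0.58) SD for one unadjusted pair; Cohen's f 0.29 (0.26) for the three-arm ANOVA, which is 0.62–0.71 (0.56–0.65) SD between extreme arms depending on the pattern of means.
3. In the Synopsis, 10.1.4 and 10.2.1, state that 47 per arm (141) is the number randomised and 39 per arm the number evaluable, tolerating at most 17% total attrition with adherence exclusions counted. If 47 evaluable are required, state that 57 to 59 per arm (171 to 177 in total) will be randomised.

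The cost is a recalculation and a text amendment. No extra subjects are needed under the first reading of 47, and 30 to 36 under the second. The restated power may be less favourable than 80%.

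### With a positive 10% margin the printed hypotheses do not express non-inferiority, and the 80% power rests on a one-sided 5% level while the decision uses a 95% CI (about 70% power at 39 per group, 78% at 47, if that CI is two-sided)

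*Combined protocol and SAP*

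**What the plan says.** Section 10.2.2 sizes the trial with an equation for two proportions, using 80% power, "a significance level of 0.05 (α) and a non-inferiority margin (δ) of 10"%. The hypotheses are "H_0: P_A - P_B \leq \delta" and "H_1: P_A - P_B > \delta", and the section then repeats the label: "Where, δ is the margin of non-inferiority". The same two lines stand in the Synopsis under Hypothesis. The quantile term in the equation is "z_{1-\alpha} + z_{B-\beta", so α enters undivided. The result is 39 per group, raised by 20% for losses to 47, or 141 in three groups.

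On the analysis side, section 10.1.2 says: "A 95% confidence interval (95% CI) will be considered for non-inferiority criteria". The statistical paragraph of the Synopsis also names a 95% CI for this purpose.

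No section gives δ a minus sign, gives values for P_A and P_B, says which groups are A and B, says whether a higher or a lower P is favourable, or says whether the 95% CI is one-sided or two-sided.

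**The concern.** Two stated items do not fit the purpose they are given.

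**The hypothesis.** Non-inferiority means ruling out that A is worse than B by as much as the margin. The printed H1 instead asks that P_A exceed P_B by more than 10 points. Read literally, two equally good dosages would almost never pass.

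**The level.** The 80% power is computed for a one-sided 5% test. A conventional two-sided 95% CI tests each side at 2.5%, so the stated power and the stated decision rule would belong to different tests.

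If this is left open, the sign, the identity of A and B and the CI level can all be chosen after the data are seen. The protocol would also report a power that its own decision rule may not have.

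**Working it through.** **Inputs from section 10.2.2:** α = 0.05 entering as z(1−α); power 80%; δ = 10%; equal groups (k = 1); 39 per group, then 47. **From section 10.1.2 and the Synopsis:** a 95% CI. **Assumed, because not stated:** P_A and P_B.

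**1. Reproducing 39.** With k = 1 the printed equation is

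n = [P_A(1−P_A) + P_B(1−P_B)] × [(z(1−α) + z(1−β)) / (P_A − P_B − δ)]².

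The quantiles are 1.6449 + 0.8416 = 2.4865. Pairs built only from the percentages printed in that section (20, 19.66 and 12.47) do not give 39. Trying P_A = 0.20 and P_B = 0.10:

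- δ = −0.10: (0.16 + 0.09) × (2.4865/0.20)² = 38.64, rounded up to **39**.
- δ = +0.10: the denominator is 0.20 − 0.10 − 0.10 = 0, so there is no solution.
- Mirror pair, P_A = 0.10, P_B = 0.20, δ = +0.10: the denominator is −0.20 and n is again 38.64. But P_A − P_B = −0.10 lies inside the printed H0, so the inequality must be reversed for this to be a powered test.

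The pair is back-solved and not unique. For example, 0.50 and 0.3247 with δ = −0.10 gives 38.28, also rounded up to 39, as does its mirror with +0.10. These two solutions show the same mismatch with the printed sign or inequality.

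The loss allowance reproduces: 39 × 1.2 = 46.8, so 47, and 3 × 47 = 141.

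**2. What the printed H1 does to equal dosages.** Assume both at 20%, 39 each, higher is better, and a two-sided 95% CI. SE = √(2 × 0.16/39) = 0.0906, and 0.10/0.0906 = 1.104.

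- Chance that the lower limit exceeds +10%: Φ(−1.104 − 1.960) = 0.1%.
- Chance that it exceeds −10%: Φ(1.104 − 1.960) = 20%.

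**3. Power at the level of the CI.** This step needs no P values. If 39 gives 80% at one-sided 5%, the standardised effect is 2.4865.

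| Per group | One-sided 5% | One-sided 2.5% (two-sided 95% CI) |
|---|---|---|
| 39 | 80% | Φ(2.4865 − 1.9600) = 70.1% |
| 47 | Φ(2.7296 − 1.6449) = 86.1% | Φ(2.7296 − 1.9600) = 77.9% |

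Here 2.7296 = 2.4865 × √(47/39). Because 39 was rounded up, the last column could be as high as 71.2% and 79.0%. For the assumed 20%/10% pair, power at 39 is 70.5%.

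**4. Size for 80% at one-sided 2.5%.** 39 × (2.8016/2.4865)² = 49.5. The assumed pair gives 0.25 × (2.8016/0.20)² = 49.06. Either way this is about 50 evaluable per group.

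**The case against.** **The sign is only notation.** A margin is often quoted as a magnitude, and section 10.2.2 calls δ a non-inferiority margin. This stands as an account of intent. A reader might infer that the trial is meant to demand superiority by 10 points. The documents do not support that: they name non-inferiority in three places, and the simplest calculation that reaches 39 uses −10%. Nor is the printed H1 superiority in both directions; if lower P is better, it shows A to be worse. The misprint still needs correcting, because it appears in both the Synopsis and section 10.2.2.

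**The 70% is not unconditional.** A reader might infer that the trial simply has 70% power. That needs the CI to be two-sided, which is usual but not stated. With a one-sided 95% bound the 80% stands. It also needs 39 per group, whereas the Synopsis and sections 10.1.4 and 10.2.1 call 47 evaluable. Both points are accepted. But 39 is the number that carries the 80% claim, and 47 is 39 plus an allowance for losses. Removing 20% from 47 leaves 37.6. Section 10.1.5 also drops subjects below 70% adherence. At 47 the figure is about 78%, still under 80%.

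**No planned test applies the rule.** The OSDI score is analysed by ANOVA or Student's t test, and no responder proportion is defined. This is true. It means that the power belongs to a comparison the plan does not otherwise specify, which is a reason to define or remove the non-inferiority wording.

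**Any power depends on P_A and P_B.** On the back-solved pair, both 80% and 70% suppose that A is truly 10 points higher than B. For equal dosages at 20% the chance is about 20%, and 80% power with a two-sided 95% CI would take 0.32 × (2.8016/0.10)² = 251.2, so 252 per group. A restated power must therefore carry its assumptions.

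**Conclusion.** The point holds. As printed, the hypotheses are not non-inferiority hypotheses in either direction. The sign or the inequality is probably misprinted, but this rests on assumed P_A and P_B and cannot be confirmed from the documents.

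The stated 80% power and the 95% CI agree only if a one-sided 95% bound (a two-sided 90% CI) is meant. Under the usual two-sided reading, power is about 70% at 39 per group and about 78% if all 47 are evaluable. Those figures take the plan's own 80% at 39 as correct and need no P values. The statement about the sign and the figures for equal dosages do depend on assumed P values.

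**What to change.** **If non-inferiority is kept.** In the Synopsis and section 10.2.2, name A and B, state P_A and P_B, and say which direction is favourable. Then print the matching null:

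- higher P better: H0: P_A − P_B ≤ −δ;
- lower P better: H0: P_A − P_B ≥ δ.

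Use one level throughout. Either state a one-sided 95% bound (90% CI) in section 10.1.2 and the Synopsis, or keep the two-sided 95% CI and restate power as about 70% at 39 and 78% at 47, conditional on the stated P_A and P_B.

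**If non-inferiority is not a goal.** Remove it from the Synopsis (both the hypotheses and the statistical paragraph), section 10.1.2 and section 10.2.2. Deletion alone would leave the sample size without a basis, so also state what the fixed 47 per group delivers for the planned OSDI comparison.

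**Cost.** Amendment wording, which section 11.2 sends through the committees and COFEPRIS, and a less favourable stated power if the two-sided CI stays. No patients are added, since each route keeps the planned number and restates what it provides.

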P_i = weight of the container delivered to the subject at the beginning

P_f = weight of the container returned by the subject

PT = weight of the dosage indicated for the intervention

$$PT = (P_g)G$$

Where:

P_g = weight of one drop of the intervention, determined by the research and development department

G = number of applications indicated for the intervention

Packaging that does not retain its physical integrity will not be considered for the calculation of adherence. In cases where the container is not returned, or it has not preserved its physical integrity, adherence will be measured only through the subject's diary

Adherence through the subject's diary will be measured as follows:

$$Ad = (Ar)100/Ai$$

Ad = Adhesion

Ar = Registered Applications

Ai = Applications indicated for the products under investigation

There is no standardized parameter to define adequate adherence, it must be defined and delineated by the objectives of the particular research. [47]

For this study, a minimum adherence of 70% will be considered to be what is necessary to meet the objectives of the research both by subject diary and by bottle weight. Therefore, subjects who have an adherence of less than 70% will not be considered for the efficacy analysis, they will only enter the safety analysis.

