10.1.4 Deviations from the statistical plan

According to the calculation of the sample size to meet the primary objective of the study, 141 evaluable subjects (47 subjects per dosage) are required. If this number is not met due to a loss of subjects greater than 20% contemplated in this protocol (loss of follow-up or withdrawal of ICF), in order to balance the treatment groups, the sponsor may replace these subjects.

The results obtained from the substituted subjects will continue to be used for safety analysis and will be part of the *Intention To Treat* population (ITT).

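### The 47 per arm covers 8 losses (17.0%), not 20%, and neither the allowance nor the replacement clauses count adherence exclusions from the primary analysis

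*Combined protocol and SAP*

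**What the plan says.** Section 10.2.2 takes 39 per arm from a two-proportion formula and adds the allowance: "the result is 39 subjects, this calculation was increased by 20% considering possible losses (8 subjects". It then concludes: "The total suggested sample size is 141 subjects (47 subjects per treatment dosage". The 47 is therefore an enrolment figure that already includes expected losses.

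Section 10.1.4 treats the same figure as the number left after losses: "141 evaluable subjects (47 subjects per dosage) are required". The synopsis and section 10.2.1 also call it evaluable. Section 10.1.4 lets the sponsor replace subjects when the number is missed because of "a loss of subjects greater than 20% contemplated in this protocol (loss of follow-up or withdrawal of ICF".

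Section 5.2.2 allows the same two kinds of subject to be replaced, with ethics committee authorisation, when balance requires it. It gives no percentage.

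On adherence, section 6.4 states that "subjects who have an adherence of less than 70% will not be considered for the efficacy analysis". Section 10.1.5 makes this the per-protocol set for the primary endpoint, and section 10.1.3 limits efficacy in a similar way.

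**The concern.** There are two separate faults.

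- **The inflation.** Raising 39 by 20% does not protect 39 against a 20% loss, because the loss acts on the larger enrolled number. The protection claimed is slightly more than the protection provided.
- **The count.** The allowance and both replacement clauses recognise only loss to follow-up and withdrawal of consent. The primary analysis also drops everyone below 70% adherence. These exclusions reduce the number behind the power statement, but they use up no stated allowance and engage no rule.

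At stake is whether the primary analysis will contain the 39 per arm on which the 80% power rests, and whether anyone is required to notice if it does not.

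**Working it through.** **Inputs.** From section 10.2.2: 39 per arm, 20%, 8 subjects, 47 per arm, 141 in total, and "considering a power of 80% (β), a significance level of 0.05 (α) and a non-inferiority margin (δ) of 10". From section 10.1.4: the threshold of more than 20%. From sections 6.4 and 10.1.5: exclusion below 70% adherence. The documents give no expected non-adherence rate.

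**Reproducing the plan.** 39 × 1.2 = 46.8, rounded up to 47, and 3 × 47 = 141. Both match. Dividing by 0.8 does not give 47.

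The 39 itself cannot be rebuilt from stated inputs. Section 10.2.2 says "a decrease in the OSDI score of 20% was considered for the formulation proposed in this protocol", which suggests 0.20 for one proportion, but the other is not given. If it is assumed to be 0.10, with the margin signed so that the denominator is 0.20, then (0.16 + 0.09) × (2.4865/0.20)² = 38.64, rounded up to 39. Nothing below depends on this; 39 is taken as given.

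**What 47 tolerates.**
- Cushion: 47 − 39 = 8, and 8/47 = 17.0%. Over the trial this is 24 of 141.
- Needed for a true 20% loss: 39/0.8 = 48.75, so 49 per arm and 147 in total (6 more).

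**The 10.1.4 threshold, if 20% is a share of those enrolled.**
- One arm: 9/47 = 19.1% does not exceed 20% and leaves 38. A tenth loss (21.3%) does exceed it.
- Whole trial: 28/141 = 19.9% does not exceed 20% and leaves 113, against 3 × 39 = 117.

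**Adding adherence exclusions.** An arm that has used its full allowance of 8 falls below 39 with the first adherence exclusion. An arm with no losses at all falls to 38 with 9 adherence exclusions, and neither replacement clause applies. The non-adherence rates in the table are assumptions.

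Power is scaled from an assumed 80% at n = 39, with the one-sided 0.05 that the plan's formula uses: Φ(2.4865 × √(n/39) − 1.6449).

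| Situation | n per arm | Power |
|---|---|---|
| Sample-size result | 39 | 80.0% |
| 9 of 47 lost | 38 | 79.1% |
| 20% loss, then 10% non-adherent: 47 × 0.8 × 0.9 = 33.8 | about 34 | about 75% |
| 20% loss, then 20% non-adherent: 47 × 0.8 × 0.8 = 30.1 | about 30 | about 70% |

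With one-sided 0.025 the figures are slightly lower: 79.0% at 38 and 69.1% at 30.

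**If 47 really must be evaluable.** 47/0.8 = 58.75, so 59 per arm and 177 in total. This is not what section 10.2.2 plans.

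**The case against.** The inflation error costs 2 subjects per arm and about one point of power, and much of the apparent gap in the rules depends on how they are read. Four stronger conclusions that a reader might draw are not supported.

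- **That losses between 17% and 20% meet no replacement rule.** Section 5.2.2 permits replacement with no percentage, so those losses can be made good. The two clauses differ and need to be reconciled.
- **That the gap between 17% and 20% is certain.** Section 10.1.4 does not define the base of its 20%. The only place where the protocol sets the allowance applies 20% to 39 and calls it 8 subjects. On that base replacement opens at the ninth loss and there is no gap.
- **That an arm can reach 37 without passing the threshold.** 47 × 0.8 is 37.6, but subjects are whole. Judged arm by arm, the most that can be lost without passing 20% is 9, leaving 38. Only a trial-wide count could allow 37 in one arm.
- **That the percentages above are the power of the primary analysis.** They are scaled from an assumed 80% at 39, on a two-proportion formula with one proportion unstated. Table 3 assigns ANOVA or a t-test to the OSDI score. They show relative loss on the plan's own scale and nothing more.

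It is also fair to say that the larger losses rest on non-adherence rates with no source in the documents. What stands is that the adherence exclusions are written into the plan, affect the primary analysis set, and appear in neither the allowance nor either replacement clause. No reading of the 20% changes that.

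**Conclusion.** Wrong as written, in a figure the plan relies on, and cheap to correct. The tolerated loss is 8 per arm (17.0%), not 20%. Taken alone this matters little: at most one subject per arm below 39 under the less favourable reading of section 10.1.4 applied by arm, and none under the other.

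The weightier fault is the omission of adherence exclusions, which can take an arm below 39 with no rule engaged. Its size is unknown. The range of about 34 to 30 per arm assumes 10% to 20% non-adherence on top of a 20% loss, and the corresponding power of about 75% to 70% further assumes exactly 80% at 39. The documents do not show that the trial will be underpowered. They show that the plan does not guard the number it depends on. The conflict over whether 47 or 39 is the evaluable number is part of the same fault.

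**What to change.** 1. In section 10.2.2, state that 47 enrolled per arm tolerates 8 exclusions from the primary analysis (17%) for any reason, including adherence below 70%, and that the stated 80% power does not hold beyond that.
2. In section 10.1.4, replace the percentage with a count: more than 8 subjects in an arm who are not in the per-protocol primary analysis set. Reconcile this with section 5.2.2 so that one rule governs replacement. State the adherence criterion once as well: section 10.1.5 asks for both bottle weight and diary, while section 10.1.3 uses the diary only when the bottle cannot be weighed, and the count depends on which applies.
3. In the synopsis and sections 10.1.4 and 10.2.1, reconcile the word evaluable with section 10.2.2, where 47 already includes the loss allowance and 39 is the evaluable number.

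**Cost.** The planned 141 does not change, but the stated tolerance drops from 20% to 17%, and several sections need edits. Replacement is not free: each one adds enrolment, and a trigger that counts adherence exclusions may lead to more of them. Replacement restores numbers only. It does not undo the selection from dropping subjects after randomisation in an open-label comparison of 2, 4 and 6 applications a day.
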